8.1.4. TRANSCRANIAL DIRECT CURRENT STIMULATION (TDCS)

We will conduct a single-center, sham-controlled, single-blinded study to prospectively investigate the neuromodulatory effects of M1 HD-tDCS in pain intensity and brain molecular neuroplasticity in a cohort of episodic migraine patients. The patients will participate in 10 daily sessions—5 daily sessions each weekday for two consecutive weeks—of either active or sham M1 HD-tDCS. (Figure 10). If a patient misses the day of a tDCS session, two tDCS sessions will occur the following day. tDCS sessions will be conducted at the University of Michigan Health System (eg, Michigan Clinical Research Center, Center for Human Growth and Development). Before and after each tDCS session patients will complete pain and mood questionnaires.

Prior to brain stimulation, the subject's scalp will be prepped in the M1 area contralateral to the subject's worst pain. The vertex will be found by measuring the midpoint between nasion and inion and the midpoint between the pre-auricular areas. Then the midpoint from the vertex to the pre-auricular point, on the side contralateral to the patient's worst pain, will be marked so that stimulation can be applied to the same spot each day. Alcohol pads will be used to wipe a 4 cm x 4 cm square centered over the motor cortex, followed by the application of approximately 6 mL of aloe vera gel to hydrate the scalp.

After 5 minutes have passed, the scalp will be wiped with gauze to remove excess gel. A perforated cloth cap with a chinstrap will then be placed on the head; this will secure plastic casings in the desired position of each electrode. Approximately 1 mL of Lectron II Conductivity Gel will be injected into each electrode casing slot. Four electrodes will be placed, with the upper anode placed on C3 and lower anode on C5, and the upper and lower cathodes placed anteriorly on FC3 and FC5, respectively, using the International Electroencephalography (EEG) 10-20 system (Zaghi et al., 2010). Approximately 1 mL of additional gel will be injected into the electrode casings. Ag/AgCI sintered ring electrodes with the rough surface directed towards the skin will be placed into the gel and held in place with plastic caps. The electrode wires will be held in place with a light adhesive tape (eg, Scotch tape), and the contact quality tested. Procedures will be reviewed with the subject before proceeding

In the active HD-tDCS group, ≤2 mA current stimulation will be applied for 20 min. For sham-controlled tDCS sessions current will be applied only for 30 sec - this is a frequent method of sham stimulation (Gandiga et al., 2006) as sensations arising from tDCS treatment occur mostly at the beginning and end of application. Nonetheless, groups will be composed by tDCS-naïve and different patients to avoid comparison between sham and active from ongoing and previous experiences.

tDCS has been used in a growing number of laboratories worldwide since 1984. Although mild adverse effects induced by (HD-)TDCS have been identified, they can be avoided if the safety guidelines are followed (Nitsche et al., 2003b). In addition to the baseline evaluation our examination will include: Patient Global Assessment, tDCS Side Effects Questionnaire, and Adverse Events Reporting. For more detailed information on the (HD-) tDCS protocols and safety use, please check the following links: tDCS (http://www.jove.com/details.php?id=2744) (DaSilva et al., 2011a) and HD-tDCS (http://www.jove.com/video/50309/technique-considerations-use-4x1-ring-high-definition-transcranial) (Villamar et al., 2013). Those peer-reviewed video-articles, created by our laboratory and collaborators, have been seen by more than 150,000 viewers and have been used as (HD)-tDCS tutorials by multiple academic centers and laboratories worldwide.

[figure not shown]

Figure 10. M1 HD-tDCS montage for homuncular head and facial region.

8.2. LABORATORY EVALUATIONS

8.2.1. CLINICAL LABORATORY EVALUATIONS

Pregnancy and drug screen testing will be performed by dipstick analysis. The results of each test will be immediately related to the subject and if positive, a repeat test may be performed on a second sample. These coded research results will be recorded in a file that is kept separately from the rest of the research data.

8.2.2. SPECIAL ASSAYS OR PROCEDURES

Serial blood samples for genetic analysis, not to exceed 70 mL per subject, will be collected during PET scanning. Details can be found in the Manual of Procedures.

8.2.3. SPECIMEN PREPARATION, HANDLING, AND SHIPPING

8.2.4. INSTRUCTIONS FOR SPECIMEN PREPARATION, HANDLING, AND STORAGE

Blood samples will be collected according to the schedule in Appendix A, and will be prepared, handled and stored following protocols set forth in the study Manual of Procedures.

8.2.5. SPECIMEN SHIPMENT

Samples will be stored on site until analysis.

9. ASSESSMENT OF SAFETY

Findings that are deemed grossly abnormal may be shared with the subject for further clinical evaluation by an outside physician. However, those findings generated in this study are not to be used for diagnostic purposes. In the same vein, interpretations of potential abnormal findings are not to be used for diagnostic purposes. The focus of this study is research, though this information may be shared in the best interest of the subject.

9.1. SPECIFICATION OF SAFETY PARAMETERS

Safety parameters for this study are comprised of the informed consent and screening processes, including the pregnancy dipstick test.

9.2. METHODS AND TIMING FOR ASSESSING, RECORDING, AND ANALYZING SAFETY PARAMETERS

9.2.1. ADVERSE EVENTS

An adverse event (AE) is any untoward or unfavorable medical occurrence in a human subject, including any abnormal sign (for example, abnormal physical exam or laboratory finding), symptom, or disease, temporally associated with the subject's participation in the research, whether or not considered related to the subject's participation in the research.

9.2.2. EXPECTED ADVERSE REACTIONS

Determination of whether a finding is clinically significant, expected AE will be made by the Principal Investigator or a Co-Investigator and will be documented on a CRF.

9.2.3. SERIOUS ADVERSE EVENTS

A serious adverse event (SAE) is one that meets one or more of the following criteria:

- Results in death
- Is life-threatening (places the subject at immediate risk of death from the event as it occurred)
- Results in inpatient hospitalization or prolongation of existing hospitalization
- Results in a persistent or significant disability or incapacity
- Results in a congenital anomaly or birth defect
- An important medical event that may not result in death, be life threatening, or require hospitalization may be considered an SAE when, based upon appropriate medical judgment, the event may jeopardize the

subject and may require medical or surgical intervention to prevent one of the outcomes listed in this definition.

9.2.4. UNANTICIPATED PROBLEMS

The Office for Human Research Protections (OHRP) considers unanticipated problems involving risks to subjects or others to include, in general, any incident, experience, or outcome that meets **all** of the following criteria:

- unexpected in terms of nature, severity, or frequency given (a) the
 research procedures that are described in the protocol-related documents,
 such as the IRB-approved research protocol and informed consent
 document; and (b) the characteristics of the subject population being
 studied;
- related or possibly related to participation in the research ("possibly related" means there is a reasonable possibility that the incident, experience, or outcome may have been caused by the procedures involved in the research); and
- suggests that the research places subjects or others at a greater risk of harm (including physical, psychological, economic, or social harm) than was previously known or recognized.

9.2.5. PROCEDURES TO BE FOLLOWED IN THE EVENT OF ABNORMAL LABORATORY TEST VALUES OR ABNORMAL CLINICAL FINDINGS

Clinical laboratory values (other than pregnancy tests results) that are noted as abnormal and clinically significant at study exit and that are changes screening values will be documented as AEs.

9.3. REPORTING PROCEDURES

9.3.1. SERIOUS ADVERSE EVENTS

Serious adverse events will be reported to IRBMED according to institutional requirements.

9.3.2. REGULATORY REPORTING FOR STUDIES NOT CONDUCTED UNDER SPONSORED IND

Reports will be submitted to NIH-NINDS on the schedule as requested.

9.3.3. OTHER UNANTICIPATED PROBLEMS

Other unanticipated problems will be reported to IRBMED on a case-by-case basis.

9.3.4. REPORTING OF PREGNANCY

If a subject has a positive pregnancy test after signing informed consent, she will be informed of this result in a confidential manner by study staff. If she wishes, her primary care physician will be notified (with her documented consent). This will be reported as an "other unanticipated problem".

9.4. SAFETY OVERSIGHT

The study will be monitored by the University of Michigan Institute for Clinical Health Research (MICHR). Adverse event/serious adverse event reporting will be to and ethics oversight will be completed by the University of Michigan Medical School IRB (IRBMED).

10. CLINICAL MONITORING

Clinical site monitoring is conducted to ensure that the rights of human subjects are protected, that the study is implemented in accordance with the protocol and/or other operating procedures, and that the quality and integrity of study data and data collection methods are maintained. Monitoring for this study will be performed by the Michigan Institute for Clinical and Health Research (MICHR). The monitor will evaluate study processes and documentation based on NINDS standards.

Details of clinical site monitoring will be documented in a Clinical Monitoring Plan (CMP) developed by MICHR. The CMP will specify the frequency of monitoring, monitoring procedures, the level of clinical site monitoring activities (e.g., the percentage of subject data to be reviewed), and the distribution of monitoring reports. Some monitoring activities may be performed remotely, while others will take place at the study site(s). Staff from MICHR will conduct monitoring activities and provide reports of the findings and associated action items in accordance with the details described in the CMP. Documentation of monitoring activities and findings will be provided to the site study team, the study Pls, and the NINDS.

10.1. SITE MONITORING PLAN

The Site Monitoring Plan (SMP) will be developed by MICHR in conjunction with the site. The SMP is a listed supplemental document (see Supplemental Documents, Page 45). These documents are relevant to the protocol, but they are not considered part of the protocol.

11. STATISTICAL CONSIDERATIONS

The main contrasts of interest will be modeled using both volume-of-interest (VOI) data with SPSS and parametric statistical maps using the SPM8 package and a general linear model for the radiotracers. The main effect of interest [effect of acute and chronic pain, opioid and psychophysiological measures, before and after 10 M1 HD-tDCS sessions (active or sham) can be modeled by t-tests or ANOVA (e.g., effect of pain), or ANCOVA (with age as covariate), with post-hoc t-tests to determine the direction and magnitude of regional changes. However, a global model will also be utilized to determine the main effects of pain, and interactions with sex and other nuisance variables (e.g., age). In that manner, we will examine the main effects of migraine and repetitive M1 HD-tDCS neuromodulation on receptor BP_{ND}, BP_{ND} changes in the thalamus and other pain-related regions in response to an experimental pain challenge, interrelationships between variables, and additional interactions with covariates of interest and nuisance variables.

Two sets of analyses will be completed with the PET data: Volume of Interest Analysis: First, we will conduct a hypothesis-driven VOI analysis in which selected brain areas are examined. It offers the advantage of a relatively narrow search within the thalamus and other regions already known to be involved in the regulation of pain and in sex differences in these phenomena (e.g., anterior cingulate, insular cortex, nucleus accumbens, amygdala, periaqueductal gray for [11C]carfentanil scans). Predefined VOIs obtained from the data acquired in previous studies (Zubieta et al., 2001; Scott et al., 2008) will be utilized for this purpose and applied to the functional image data in stereotactic space. The VOIs will then be transferred to the μ -opioid receptor BP_{ND} Statistical Parametric Mapping: In subsequent analyses, statistical parametric maps will be obtained using whole brain image subtraction routines utilizing the images warped to stereotactic coordinates, as above. SPM analyses will be employed for the radiotracer, as shown in the Preliminary Data. Differences between conditions and subject groups will then be mapped into stereotactic space using t-maps of statistical significance and SPM8 and Matlab software, using a general linear model and correction for multiple comparisons (Friston et al., 1995). These maps are displayed superimposed over the anatomically standardized T1-weighted MRI of the subjects. This second analysis does not assume that specific regions are involved selectively, and a brain-wide search is performed on a voxel-by-voxel basis. Only gray matter pixels and regions with specific binding are included in the statistical parametric analyses (voxels with BP_{ND} values > 0.2) (Wager et al., 2007). For each subtraction analysis, one- or two-sample t-statistic values are calculated for each pixel using a pooled smoothed variance across voxels (Worsley et al., 1992). Areas of significant differences are detected using a statistical threshold that controls a Type-I error rate at p = 0.05 for multiple comparisons, which is estimated using the Euler characteristic (Worsley et al., 1992) based on the number of pixels in the gray matter and image smoothness (Friston et al., 1991). We will also use a multiple comparisons procedure that controls the false discovery rate (FDR; (Genovese et al., 2002), particularly in the case of preliminary analyses (years 2-3) that would not be fully powered for standard multiple comparisons

correction. The standard Euler characteristic method described above controls the Family-wise Type-I error rate for any false positives whatsoever.

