3.4. SECONDARY OUTCOME MEASURES

Our hypothesis is that 10 daily sessions of active M1 HD-tDCS modulation will induce analgesic after-effect in clinical and experimental pain measures. The focused targeting of M1 with HD-tDCS will lead to precise sensory-discriminative modulation of pain (area and intensity). This will be evidenced in our questionnaires, tracking tools, and quantitative sensory tests.

We hypothesize that after 10 M1 HD-tDCS sessions there will be an increase in μ OR BP_{ND} (return toward healthy control values) in the thalamus and other pain-related brain areas in migraineurs at follow up, along with reductions in clinical/experimental pain measures.

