5.4. TREATMENT ASSIGNMENT PROCEDURES

5.4.1. RANDOMIZATION PROCEDURES

Participants initially will be screened by phone. After clinical exam and diagnosis of episodic migraine (confirmed by IHS/ICHD-3-beta criteria) participants will be randomized to the treatment HD-tDCS or sham groups using the Taves covariate adaptive randomization method. Using this method, a new participant will be sequentially assigned to a group based upon the previous assignments of other participants and certain covariates. The first eight migraine participants will be randomized by coin flip and the remaining migraine participants will be randomized by age and gender, following the Taves covariate adaptive randomization protocol. Healthy volunteers will be age- and gender-matched to the earlier enrolled participants.

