Potential pitfalls and alternative strategy: Regarding possible negative results we have to explore other scenarios: First, our hypothesis was wrong. However, this is unlikely due to extensive data from our group showing decreased levels of μOR BP_{ND} in chronic pain, including our initial migraine and allodynia data (DosSantos et al., 2012; DaSilva et al., 2014a; Nascimento et al., 2014a). Nonetheless, if the migraine mechanisms are not through a change in the μ-opioid system we need to explore alternative mechanisms in the future, such as the glutaminergic and GABA systems—data which will also be acquired during this study (see Aim3 alternative strategy)— hence, the results will still be interesting to report and investigate further. Second, μOR BP_{ND} levels at baseline will not be correlated with pain levels (also unlikely based on our data) (DaSilva et al., 2014a; DosSantos et al., 2014a). Although we are powered to perform all the analyses in this study, correlation analysis is a test that has low power. In the case of a statistical trend for a correlation, we will look at thalamus and other pain-related regions, and consider increasing the sample size by 20% and then describing these specific results as exploratory. We will also use different pain ratings (e.g., Pain Trek).

Does M1 HD-tDCS have modulatory effect on experimental and clinical measures in migraine?

Aim 2. To determine whether 10 daily sessions of M1 HD-tDCS have modulatory effect on clinical and experimental pain measures in migraine patients.

Our hypothesis is that 10 daily sessions of active M1 modulation, as compared to sham, will induce a greater analgesic after-effect in clinical and experimental pain measures. The focused targeting of M1 with HD-tDCS will lead to more precise sensory-discriminative modulation of pain (pain area and intensity). This will be evidenced in our

questionnaires (e.g., McGill, PANAS), pain tracking tools, and quantitative sensory tests.

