Feasibility: (Aim2.2) In order to evaluate the analgesic effect of focally targeted M1 modulation, we have developed a novel M1 HD-tDCS montage with 2 x 2 electrode design, which we tested on a cohort of patients with another chronic trigeminal pain illness, temporomandibular disorder (TMD). Our computational model simulated our montage's current flow through tissues captured with 3D imaging, accounting for the tissue type, tissue shape, tissue resistance, electrode positioning, and strength of the current. Greatest density was focused on the lower region of the precentral gyrus/sulcus, targeting the putative homuncular craniofacial M1 region and immediately within the HD-tDCS 2 x 2 electrodes (Figure 16). This is the region where invasive motor cortex stimulation produces maximal analgesic effect for head and facial pain (Nguyen et al., 1999). We screened 78 patients for this study, and of those 24 (30.8%) were randomized, with 12 per group. All patients completed the active or placebo 5daily sessions of M1 HD-tDCS study according to the protocol. There were statistically significant between groups differences for sensorimotor measurements, including VAS 50% responders (p=0.04) at one-month follow-up (Table 2), pain free mouth opening at one-week follow-up (p<0.01), and most important: improvement of contralateral sensory-discriminative pain measures as collected by PainTrek (e.g., pain intensity, area and their summation), not ipsilateral pain measures, during the treatment week (p<0.01) (Table 3). In addition, we found "no" significant evidence that mood changes differed overall between the groups, as evaluated by the Positive and Negative Affect Scale (PANAS), indicating that our focused M1 HD-tDCS montage selectively modulated sensorimotor outcomes.

Potential pitfalls and alternative strategy: There is a possibility that at the end of the tDCS and PET study we get negative pain measures results. In this case, our 2nd

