hypothesis was wrong, and only modulation of the pain-related neural networks will be seen in migraineurs (Aim3); however, this is unlikely based on previous successful experience with M1-tDCS and chronic migraine (DaSilva et al., 2011c), and experimental trigeminal pain (DosSantos et al., 2014b). A recent meta-analysis study in non-invasive M1 stimulation for chronic pain indicated an effective size of -0.86 (95% C.I., -1.54, -0.19) on the VAS (Zaghi et al., 2011). Another issue is the accuracy on targeting M1 in our montage. It is important to note that current can concentrate at distinct gyri/sulci sites so current flow, and thus brain activation, is not homogenous across an area of stimulation (Datta et al., 2009). Still, when external landmarks are used to target brain regions with HD-tDCS, computational models improve accuracy, but they are prediction models. In order to address this issue we will confirm the M1 location by using transcranial magnetic stimulation (Zaghi et al., 2010).

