11.2. SAMPLE SIZE CONSIDERATIONS

Taking into consideration a possible 20% dropout during the study, our sample size of 30 patients per group is a conservative number. For comparing two groups in Aim1 and Aim2, a sample size of 24 in each group will have 80% power to detect an effect size of 1.2 using a two-group t-test with a 0.05 two-sided significance level. For Aim3, baseline vs placebo/active M1 HD-tDCS, a sample size of 24 will have 80% power to detect an effect size of 0.8 using a paired t-test with a 0.05 two-sided significance level, allowing a wide range (0.1 to 1.0) of observable correlations within pairs.

Using the previous study, we approximated the SD as 20%/4 = 5% (range/4), and this gives us a detectable percentage change of 5*0.8=4 or higher.

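### In the supplied protocol, no passage names baseline pain as a covariate for the secondary Aim 2 active-versus-sham comparison; stating a baseline-adjusted ANCOVA is a low-cost improvement.

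*Combined protocol and SAP*

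**What the plan says.** Section 3.4 lists the pain hypothesis among the secondary outcomes: "Our hypothesis is that 10 daily sessions of active M1 HD-tDCS modulation will induce analgesic after-effect in clinical and experimental pain measures". Section 11.1 makes it a between-arm comparison: "active M1 modulation, as compared to sham, will induce a greater analgesic after-effect in clinical and experimental pain measures".

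In Section 11.1, Aims 1 and 3 each have an analysis paragraph naming a mixed model. The Aim 2 text has a hypothesis, feasibility data and pitfalls, but no analysis paragraph. Three places bear on how Aim 2 would be analysed:

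- Section 11, mainly about imaging, includes psychophysiological measures before and after the sessions, "active or sham) can be modeled by t-tests or ANOVA (e.g., effect of pain), or ANCOVA (with age as covariate". It then commits to a global model with sex and nuisance variables such as age, and leaves further covariates of interest open.
- Section 11.2 sizes the comparison on a two-group t-test, "For comparing two groups in Aim1 and Aim2, a sample size of 24 in each group", without saying whether post-treatment or change scores are compared.
- The Aim 2 feasibility text reports that the group's earlier chronic-migraine tDCS trial tested a time-by-group interaction by ANOVA.

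Pre-treatment pain is recorded. Section 8.1.4 states: "Before and after each tDCS session patients will complete pain and mood questionnaires". Appendix A also marks the VAS, short-form McGill and GeoPain at Screening and at PET/MRI #1. Section 5.4.1 allocates by coin flip for the first eight patients, after which "the remaining migraine participants will be randomized by age and gender". Section 11.6 defers the final analysis to a Statistical Analysis Plan, which the Supplemental Materials page lists as a separate document.

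**The concern.** Three analyses of the same pain score remain open: a post-score comparison, a change-score comparison (or its time-by-group equivalent), and ANCOVA with age. They differ in precision, and which is better depends on r. A post-score test wastes information when r is high; a change score adds noise when r is low. ANCOVA on the pre-treatment score is near or above the better of the two in either case, and it corrects chance imbalance in baseline pain.

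The open choice also matters because several pain scores are taken at several visits, and Section 11.3 plans a look after one year that may lead to adjustments. If the model is not fixed beforehand, it can be chosen after the results are known.

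**Working it through.** **The plan's own figure.** Section 11.2 gives 80% power for 24 per group at an effect size of 1.2, two-sided 0.05, two-group t-test. The exact noncentral t gives 98.3%. The stated 80% appears with 12 per group (80.2%); 24 per group has 80% power for d = 0.826. The dropout step is consistent: 30 × (1 − 0.20) = 24. The mismatch is a separate matter, and nothing below rests on it.

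**Inputs.** n = 24 per arm and two-sided 0.05 (Section 11.2). d = 1.2 (Section 11.2). d = 0.86, from the chronic-pain meta-analysis cited in Section 11.1, which "indicated an effective size of -0.86 (95% C.I., -1.54, -0.19) on the VAS", read here as a standardised difference. Assumptions: r = 0.1, 0.3, 0.5, 0.7; d in follow-up SD units; equal SDs before and after; age and sex balanced by the allocation and not prognostic.

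**Formulas.**
- Post-score: noncentrality d × √(24/2), 46 df. At 0.86: 0.86 × 3.464 = 2.98.
- Change score: replace d by d/√(2(1 − r)). At 0.86 this is 0.641, 0.727, 0.860, 1.110. With one pre and one post value, a time-by-group ANOVA is this same test.
- ANCOVA on arm, baseline, age and sex: 43 df. The variance of the arm difference is (1 − r²) × (2/24) × (1 + 1/44) on average; the last factor is the loss to chance imbalance in baseline. At d = 0.86 and r = 0.5 the noncentrality is about 0.86/√(0.75 × 0.0833 × 1.0227) = 3.40. Powers and detectable effects below are averaged over random baseline draws.
- 95% CI half-width: t quantile × standard error. Post-score: 2.013 × √(2/24) = 0.58 SD. The change score multiplies this by √(2(1 − r)). ANCOVA uses 2.017 × √((1 − r²) × 0.0833 × 1.0227).

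**Results** (each cell: post-score / change score / ANCOVA).

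| r | d detectable at 80% | Power %, d = 0.86 | Power %, d = 1.2 | CI half-width, SD |
|---|---|---|---|---|
| 0.1 | 0.83 / 1.11 / 0.83 | 83.1 / 58.5 / 82.5 | 98.3 / 85.8 / 98.1 | 0.58 / 0.78 / 0.59 |
| 0.3 | 0.83 / 0.98 / 0.80 | 83.1 / 69.3 / 85.5 | 98.3 / 93.0 / 98.8 | 0.58 / 0.69 / 0.56 |
| 0.5 | 0.83 / 0.83 / 0.73 | 83.1 / 83.1 / 91.4 | 98.3 / 98.3 / 99.6 | 0.58 / 0.58 / 0.51 |
| 0.7 | 0.83 / 0.64 / 0.60 | 83.1 / 96.4 / 98.1 | 98.3 / >99.9 / >99.9 | 0.58 / 0.45 / 0.42 |

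At r = 0 and d = 1.2, the change-score test has 82% power. ANCOVA overtakes the post-score test at r of about 0.16.

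**If age and sex were left to chance instead.** ANCOVA power at d = 0.86 would be 80.7, 83.9, 90.1 and 97.6%, and the crossover would move to about r = 0.26.

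**The case against.** The strongest reply is that a reader might infer from Section 11 that the plan ignores baseline pain, and the documents do not support that. The before-and-after wording points to a pre/post contrast, and the time-by-group ANOVA of the group's earlier trial uses the baseline score. The global model is a commitment and already brings in sex and age. The separate SAP may name the model. All of this stands, so the point is limited to the supplied text not naming baseline pain as a covariate.

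A second reply is that the numerical gain is conditional. That also stands. r is undocumented, and 0.86 comes from a meta-analysis in chronic pain with a wide interval. If 1.2 is meant in change-score SDs, the change-score test has 98% power at every r. It would be equally wrong to argue that r must be low because patients are attack-free: the 48-hour rule in Section 8.1.3 applies to scans, although Section 7.4 lets the Week 1 visit be combined with one.

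A third reply is that choosing a lead outcome is a matter of preference. One could infer that VAS at Month 1 is the natural lead from the group's HD-tDCS trial, which reported differences "including VAS 50% responders (p=0.04) at one-month follow-up". That trial was in temporomandibular disorder, with 12 per group and five sessions. The same passage gives most weight to the PainTrek measures, so it does not settle the choice.

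What survives is the open choice between change score, post score and age-only ANCOVA, and the fact that baseline adjustment is the safe choice when r is unknown.

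**Conclusion.** The point holds as an optional improvement to a secondary analysis. At d = 0.86, baseline-adjusted ANCOVA gains from about 2 points (r = 0.7) to 24 points (r = 0.1) over a change-score test. Against a post-score test it ranges from a loss of under 1 point (r = 0.1) to a gain of 15 points (r = 0.7). At the planning effect of 1.2 it moves power only from 98% to between 98% and above 99% relative to a post-score test, so this is not a claim that Aim 2 is underpowered.

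The practical value is a narrower interval over most of the range of r, protection if the true effect is below 1.2, and a model fixed before the data are seen. The sizes rest on the assumed r, on d in follow-up SD units with equal pre and post SDs, and on age and sex being balanced and non-prognostic. The separate SAP could already resolve the matter.

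**What to change.** Add an analysis paragraph for Aim 2 to Section 11.1. For each pain score, state ANCOVA of the post-treatment score on arm, the same pre-treatment score, age and sex, the last two because they drive the allocation. Report the adjusted active-minus-sham difference with its 95% CI, and keep the unadjusted test as supportive.

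Name in advance one lead score, one visit and one baseline rating; which ones is for the investigators to decide. The choice of baseline needs care. Questionnaire ratings exist at Screening, at PET/MRI #1 and before the first session. Section 5.3 places QST at screening, whereas Appendix A marks it only at the two PET/MRI visits. Label other scores and visits, or a repeated-measures model across follow-up, as supportive. If the separate SAP already does this, align Section 11 with it.

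The cost is wording and three degrees of freedom, with no new data or visits. At r = 0.1 this is under 1 point of power against a post-score test with age and sex balanced, or 2 to 3 points if they were left to chance.
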